9.2. Setting

The source population will be health plan enrollees from data RPs that contribute data from claims and electronic health records to the FDA Sentinel System. The planned data sources for the study are CVS Health (Aetna Research Database), Carelon Research (formerly HealthCore), HealthPartners, Humana, and Optum Research Database. The participation of these data sources will be confirmed before the SAP is finalized, and additional data sources may be added.

9.2.1. Study population eligibility criteria

9.2.1.1. Population to assess general safety events

Individuals will be eligible for analysis of general safety events (which will use an SCRI design) if they meet the following criteria:

1. Aged ≥ 6 months for at least 1 day during the study observation period.
2. Have received a dose of Pfizer-BioNTech bivalent COVID-19 Vaccine. Note that individuals will be eligible regardless of the brand(s) of any COVID-19 vaccines received before Pfizer-BioNTech bivalent COVID-19 Vaccine.
3. Have had continuous medical and pharmacy insurance coverage for at least 12 months before receipt of the Pfizer-BioNTech bivalent COVID-19 Vaccine, or from birth until receipt of the Pfizer-BioNTech bivalent COVID-19 Vaccine (for individuals aged younger than 12 months at the time of receipt of the vaccine). For children aged younger than 12 months at the time of vaccination, a delay in enrollment (duration to be specified in the SAP) from birth will be allowed.

Additionally, for analysis of each safety event, individuals will be required to meet the following criteria:

4. Have experienced the event of interest during the risk or control intervals (see Section 9.3.2.1 for event-specific risk interval definitions; event-specific control intervals will be defined in the SAP)
5. Did not experience the specific safety event of interest during the pre-event washout period (the event-specific washout periods will be defined in the SAP)
6. Have continuous health plan enrollment from the start of the event-specific risk interval until the end of the event-specific control interval (for individuals who live until the end of the control interval) or until death (for individuals who die before the end of the control interval)

7. Have received no additional doses of COVID-19 vaccine other than Pfizer-BioNTech bivalent COVID-19 Vaccine during the risk interval and no additional doses of COVID-19 vaccine of any brand through the end of the control interval. Additional doses of Pfizer-BioNTech bivalent COVID-19 Vaccine will be allowed during the risk interval to enable the capture of more than 1 dose administered in a short timeframe, as the vaccine is currently approved for use as more than 1 dose in the primary series.

The index date (ie, date of cohort entry) will be the date of receipt of Pfizer-BioNTech bivalent COVID-19 Vaccine.

All individuals receiving Pfizer-BioNTech bivalent COVID-19 Vaccine will be assumed to have met the eligibility criteria to receive the vaccine under the FDA authorization (see Section 7 for summary of FDA authorizations of Pfizer-BioNTech bivalent COVID-19 Vaccine, which have changed over the course of the study period). This assumption will be made because requiring the prerequisite number and types of COVID-19 vaccine doses before receipt of Pfizer-BioNTech bivalent COVID-19 Vaccine is anticipated to require health plan enrollment from the date of an individual's initial eligibility for COVID-19 vaccination, which would severely reduce the number of individuals eligible for the study and potentially lead to imprecise comparative risk estimates and selection bias.

Given the FDA authorizations of Pfizer-BioNTech bivalent COVID-19 Vaccine, it is anticipated that some individuals may contribute more than 1 dose of Pfizer-BioNTech bivalent COVID-19 Vaccine to the analyses. Details on how subsequent doses of Pfizer-BioNTech bivalent COVID-19 Vaccine will be handled in the analysis will be described in the SAP.

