7. RATIONALE AND BACKGROUND

On 31 August 2022, the US FDA authorized Pfizer-BioNTech bivalent COVID-19 Vaccine (Original and Omicron BA.4/BA.5) for emergency use as a single booster dose for the prevention of COVID-19 (coronavirus disease 2019) in individuals aged 12 years and older (FDA, 2023b). On 12 October 2022, the FDA subsequently authorized the vaccine for use as a single booster dose in individuals aged 5-11 years. Additionally, on 08 December 2022, the FDA authorized Pfizer-BioNTech bivalent COVID-19 Vaccine to be used as a third dose in the primary series in children aged 6 months through 4 years, following 2 doses of Pfizer-BioNTech monovalent COVID-19 Vaccine (Original). On 14 March 2023, the FDA authorized Pfizer-BioNTech bivalent COVID-19 Vaccine for use as a single booster dose in children aged 6 months through 4 years who had previously completed a 3-dose primary series of Pfizer-BioNTech monovalent COVID-19 Vaccine (FDA, 2023a).

PFIZER CONFIDENTIAL

CT24-WI-GL02-RF02 4.0 Non-Interventional Study Protocol Template For Secondary Data Collection Study

01-Jun-2022

Page 20 of 62

On 18 April 2023, the FDA amended the EUA for Pfizer-BioNTech COVID-19 Vaccine to simplify the vaccination schedule, such that the current bivalent vaccine was to be used for all initial and subsequent doses administered to individuals aged 6 months and older. At the same time, the original Pfizer-BioNTech monovalent COVID-19 Vaccine was no longer authorized for use (FDA, 2023b). Updates to simplify the vaccination schedule were as follows:

- For unvaccinated individuals, Pfizer-BioNTech bivalent COVID-19 Vaccine was authorized as a 3-dose series in individuals aged 6 months through 4 years and as a single dose in individuals aged 5 years and older.
- For individuals aged 6 months through 4 years who had previously received 1 dose of monovalent vaccine, Pfizer-BioNTech bivalent COVID-19 Vaccine was authorized to be used as 2 additional doses; for individuals aged 6 months through 4 years who had received 2 or 3 doses of monovalent vaccine, Pfizer-BioNTech bivalent COVID-19 Vaccine was authorized to be used as a single dose.
- For individuals aged 5 years and older who had previously received 1 or more doses of monovalent COVID-19 vaccine, a single dose of Pfizer-BioNTech bivalent COVID-19 Vaccine was authorized.

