9. RESEARCH METHODS

9.1. Study design

The study will use a SCRI design to assess general safety events (ie, non-pregnancy related safety events of interest, including myocarditis/pericarditis; see Section 9.3.2.1 for list of specific events) among the general population and specific subpopulations of interest (immunocompromised individuals, pregnant women, and the pediatric population). A cohort design will be used to assess pregnancy and birth outcomes.

For general safety events, the SCRI design (Figure 1) will compare the incidence of safety events of interest in a predefined post-vaccination risk interval with that in a self-matched post-vaccination control interval, among individuals who have received Pfizer-BioNTech bivalent COVID-19 Vaccine. A buffer period (in which incidence will not be assessed) will be incorporated between the risk and control intervals to avoid any carry over effects from the risk interval into the control interval. Control intervals for each outcome will be defined to reflect the baseline risk of the outcome, and buffer and control intervals will take into consideration the duration of the risk interval, potential seasonality of the outcome, and the recommended timing between the initial bivalent vaccine dose and additional COVID-19

[figure not shown]
PFIZER CONFIDENTIAL

CT24-WI-GL02-RF02 4.0 Non-Interventional Study Protocol Template For Secondary Data Collection Study
01-Jun-2022

Page 23 of 62

vaccine doses. Additionally, as an eligibility criterion for each specific safety event of interest, a set period of time prior to the event date (washout period) in which the individual may not have experienced the safety event of interest will be defined to more plausibly identify incident cases.

Figure 1. Self-controlled risk interval design to assess general safety events

[figure not shown]
COVID-19 = coronavirus disease 2019.

This study design is appropriate for studying acute events with well-defined risk periods. A strength of the SCRI design is that it avoids confounding due to time-invariant confounders (including prior history of COVID-19 vaccination, which may be challenging to identify in claims administrative data). Additionally, because the SCRI design only includes vaccinated individuals, it avoids misclassification of unexposed status arising from incomplete capture of COVID-19 vaccination in claims data.

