9.2.2. Pregnancy outcomes (spontaneous abortion, stillbirth, and preterm birth)

Separate cohorts of pregnant women exposed to Pfizer-BioNTech bivalent COVID-19 Vaccine (exposed cohort) and pregnant women not exposed to any COVID-19 vaccine (unexposed cohort) will be formed for the final analysis of pregnancy outcomes (Table 1). To be eligible for either cohort, pregnant women must be enrolled from 12 months before cohort entry (ie, the index date) until the end of pregnancy.

Table 1. Cohort definitions for analysis of pregnancy outcomes

Cohort	Eligibility criteria	Index date
Exposed cohort	
 Receipt of a dose of Pfizer-BioNTech bivalent COVID-19 Vaccine in the exposure window (as defined in Table 3) Continuous enrollment in the 12 months before the index date until end of pregnancy 	
 Date of vaccination
Unexposed cohort	
 No receipt of any COVID-19 vaccine in the exposure window (as defined in Table 3) Continuous enrollment in the 12 months before the index date until end of pregnancy Matched individually (in a ratio of at least 1:1) to exposed women on estimated pregnancy start (LMP, within pre-specified calendar intervals), maternal age, and US state (if feasible, or broader geographic region if not feasible) 	
 Equivalent of the gestational age at vaccination (in days) in the exposed match. For example, if an exposed individual was vaccinated at 28 weeks and 3 days of gestation, the index date for unexposed matches would be set to 28 weeks and 3 days after their LMP.

COVID-19 = coronavirus disease 2019; LMP = date of last menstrual period; US = United States.

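### The self-controlled analysis sets no minimum time since an earlier monovalent or other-brand COVID-19 dose, so carry-over from a recent dose can fall only in the risk interval and can bias 28- and 42-day IRRs upward

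*Protocol*

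**What the plan says.** Section 9.2.1.1 of the Protocol defines who enters the self-controlled risk interval (SCRI) analysis. On earlier vaccination, criterion 2 says: "Note that individuals will be eligible regardless of the brand(s) of any COVID-19 vaccines received before Pfizer-BioNTech bivalent COVID-19 Vaccine". It is silent on how long ago that vaccine was given.

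The other criteria do not fill the gap. Criterion 7 begins: "Have received no additional doses of COVID-19 vaccine other than Pfizer-BioNTech bivalent COVID-19 Vaccine during the risk interval". It goes on to bar any brand through the end of the control interval, so it looks forward from the index dose. It makes one exception: "Additional doses of Pfizer-BioNTech bivalent COVID-19 Vaccine will be allowed during the risk interval to enable the capture of more than 1 dose". Criterion 5 is a washout for the event, not for a vaccine: "Did not experience the specific safety event of interest during the pre-event washout period". Section 9.2.1.1 also defers one dosing question: "Details on how subsequent doses of Pfizer-BioNTech bivalent COVID-19 Vaccine will be handled in the analysis will be described in the SAP".

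Sections 9.1 and 9.3.2.1 place the control interval after the risk interval. The buffer between them is meant to stop carry-over from risk to control. Section 9.1 says that the SCRI design "avoids confounding due to time-invariant confounders (including prior history of COVID-19 vaccination, which may be challenging to identify in claims", and Section 9.9 repeats the point.

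Section 7 describes mixed series at 6 months through 4 years. One is a bivalent third dose after two monovalent doses. In another, for children "who had previously received 1 dose of monovalent vaccine, Pfizer-BioNTech bivalent COVID-19 Vaccine was authorized to be used as 2 additional doses".

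For pregnancy outcomes, Table 1 admits an exposed woman on "Receipt of a dose of Pfizer-BioNTech bivalent COVID-19 Vaccine in the exposure window". An unexposed woman may have no COVID-19 vaccine of any kind in that window. Table 2 has the same structure for birth outcomes. For pregnancy outcomes, Table 4 ends follow-up at a later COVID-19 dose that is not the study vaccine.

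**The concern.** The SCRI removes what is constant over a person's observation time. Having been vaccinated a year ago is constant. The acute effect of a dose given three weeks before the index dose is not: it is present early in the risk interval and gone by the control interval. Because the control interval is always later, this effect cannot balance out. It would be credited to the bivalent vaccine.

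The criteria are also asymmetric. A monovalent or other-brand dose one day after index removes the person from the analysis, while the same dose one day before index does not, although the two contaminate the risk interval almost equally.

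The exposure is mainly at 6 months through 4 years, where Section 7 describes monovalent-then-bivalent series. Convulsions and Kawasaki disease are analysed only in that age band, and both have a 1-42 day risk interval (Table 5).

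The pregnancy cohorts show a parallel asymmetry. An earlier COVID-19 vaccine other than the study vaccine is tolerated in an exposed woman, but disqualifies an unexposed one and ends follow-up if it comes later.

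**Working it through.** **The plan's own figure.** Table 8 gives power 0.86 for 80 events, IRR 2.0, two-sided alpha 0.05, and equal risk and control intervals. The signed-root likelihood formula for self-controlled designs, with r = 0.5, b = ln(IRR) and q = r·IRR/(r·IRR + 1 − r), is:

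- A = 2[q·b − ln(r·IRR + 1 − r)] = 2[0.6667 × 0.6931 − ln 1.5] = 0.1133
- B = (b²/A)·q(1 − q) = (0.4805/0.1133) × 0.2222 = 0.943
- Power = Φ[(√(80 × 0.1133) − 1.96)/√0.943] = Φ(1.08) = 0.860

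All 24 cells of Table 8 reproduce to within 0.01. The power table is sound and is used below only to gauge consequences.

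**Inputs for carry-over.**

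- W, the risk interval in days: 7, 28 or 42 for most events (Table 5).
- g, the gap from the earlier dose to index: not in the Protocol, so a range is shown.
- s, the share of vaccinees with such a gap: not in the Protocol, assumed.
- R, the rate ratio of the earlier dose for the event: not in the Protocol, assumed.

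**Overlap.** If the earlier dose acts for the same W days, its risk period ends on index day W − g. It covers max(0, W − g) days of the risk interval and no day of the control interval at any gap.

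**Expected IRR when the true bivalent IRR is 1**, with a constant excess over the W days:

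IRR = 1 + s(R − 1)(W − g)/W, and 1 when g ≥ W.

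For W = 42, g = 21, R = 2:

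- s = 0.25: 1 + 0.25 × 1 × 21/42 = 1.125, or 1.13
- s = 0.5: 1 + 0.5 × 1 × 21/42 = 1.25

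The full range at R = 2 is:

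| W | g | Overlap | s = 0.25 | s = 0.5 | s = 1 |
|---|---|---|---|---|---|
| 42 | 7 | 35/42 | 1.21 | 1.42 | 1.83 |
| 42 | 14 | 28/42 | 1.17 | 1.33 | 1.67 |
| 42 | 21 | 21/42 | 1.13 | 1.25 | 1.50 |
| 42 | 28 | 14/42 | 1.08 | 1.17 | 1.33 |
| 42 | 35 | 7/42 | 1.04 | 1.08 | 1.17 |
| 42 | ≥ 42 | 0 | 1.00 | 1.00 | 1.00 |
| 28 | 14 | 14/28 | 1.13 | 1.25 | 1.50 |
| 28 | 21 | 7/28 | 1.06 | 1.13 | 1.25 |
| 28 | ≥ 28 | 0 | 1.00 | 1.00 | 1.00 |

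At W = 42 and g = 21, R = 1.5 with s = 0.5 gives 1.13, and R = 3 with s = 0.5 gives 1.50. If R = 1, every entry is 1.00. For myocarditis/pericarditis (W = 7), the overlap is zero at any gap of 7 days or more.

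**Consequence.** With 80 events and equal intervals, the chance of a significant IRR above 1 under a true null is nominally 2.5%. It becomes about 8% at an expected IRR of 1.125 and about 17% at 1.25.

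**The case against.** A reader might infer that the IRR in young children is inflated as a matter of fact. The Protocol does not support that. It gives no interval between an earlier dose and the index dose, no share of children with short gaps, and no evidence that an earlier dose raises the risk of convulsions or Kawasaki disease. Without all three there is no bias.

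The remark in criterion 7 about several doses close together is not evidence of short gaps either. It concerns bivalent doses after index, whereas the issue here is a different vaccine before it. Criterion 2 speaks of brand only; that timing is unrestricted follows from the absence of a gap criterion. Repeat bivalent doses are expressly left to the SAP and are no part of this point. They could also bias the other way: a second bivalent dose on day 21 would act on days 22-63, into the buffer and possibly the control interval, lowering the IRR.

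The window for one sequence is short. Two bivalent doses after one monovalent dose became possible with the 18 April 2023 amendment, when the Pfizer-BioNTech monovalent vaccine lost authorization (Section 7). If vaccination followed the authorization, as Section 9.2.1.1 assumes, a gap under 42 days on that route needs an index date before 30 May 2023. The other route, a bivalent third dose from 8 December 2022, has no interval stated.

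Finally, Section 9.9 concedes that the SCRI can suffer time-varying confounding and leaves buffer and control intervals to the SAP to limit it by keeping observation short.

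All of this limits the claim to a possible bias of unknown size, but it does not remove it. A shorter observation time leaves the overlap in place because the control interval still comes last. The handling of an earlier monovalent or other-brand dose is not among the items that Section 9.2.1.1 defers; Sections 9.1 and 9.9 treat prior vaccination as already dealt with by the design.

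**Conclusion.** The point holds as a gap in eligibility that can bias the IRR upward for 28- and 42-day events, mainly at 6 months through 4 years. On the assumed inputs W = 42, g = 21 and R = 2, a true IRR of 1 becomes 1.13 at s = 0.25 and 1.25 at s = 0.5. It is 1.00 if the gap reaches the risk interval or the earlier dose has no effect. Gap, share and rate ratio are all assumptions. Myocarditis/pericarditis is not affected at gaps of 7 days or more, nor is any listed event at 42 days or more.

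The statement that the design removes prior vaccination as a time-invariant confounder is too broad: it does not cover a dose within the event's risk interval before index.

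The pregnancy asymmetry is plain from Tables 1, 2 and 4. Its size cannot be given, because the Protocol does not say how often two different COVID-19 vaccines fall in one exposure window.

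This is a low-cost improvement, not a demonstrated error in the estimates.

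**What to change.** 1. In Section 9.2.1.1, add an event-specific criterion: no recorded monovalent or other-brand COVID-19 vaccine within W days before the index dose, W being that event's Table 5 risk interval. Report results that include the excluded doses as a sensitivity analysis. Leave repeat bivalent doses to the SAP. A single 42-day rule for every event would be wider than needed and would discard myocarditis/pericarditis data without benefit; adding the buffer is also unnecessary, since a gap of W days already brings the overlap to zero.
2. In Tables 1 and 2, require that exposed women have no COVID-19 vaccine other than the Pfizer-BioNTech bivalent vaccine in the exposure window before their bivalent dose. This matches the unexposed criterion and, for pregnancy outcomes, the Table 4 censoring rule.
3. In Sections 9.1 and 9.9, qualify the statement: prior vaccination counts as time-invariant only if the last dose precedes index by at least the event's risk interval.

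The look-back fits within enrollment already required (12 months, or from birth, subject to the permitted enrollment delay in infants). The expected cost is a small loss of index doses, mainly in young children. Within an affected analysis the loss is about s, so it is large only where the potential bias is also large. Only recorded doses can be removed, so incomplete vaccine capture leaves some overlap.

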9.2.1.2. Population to assess pregnancy and birth outcomes

Pregnant women aged between 12-55 years will be eligible for inclusion in the final analysis of pregnancy and birth outcomes if they had a recorded pregnancy outcome (eg, live birth, stillbirth, spontaneous abortion, ectopic pregnancy, pregnancy termination) during the study period. As pregnancy status is not directly recorded in Sentinel data sources, an algorithm (to be defined in the SAP) that incorporates diagnosis and/or procedure codes will identify pregnancy episodes and pregnancy outcomes as well as the estimated start (estimated LMP) and end of pregnancy. Livebirth pregnancies identified in maternal data will be linked with infant data to identify birth outcomes during the first year of life (Sentinel, 2019). Additional cohort eligibility criteria are described below for each of the pregnancy and birth outcomes.

9.2.2. Pregnancy outcomes (spontaneous abortion, stillbirth, and preterm birth)

Separate cohorts of pregnant women exposed to Pfizer-BioNTech bivalent COVID-19 Vaccine (exposed cohort) and pregnant women not exposed to any COVID-19 vaccine (unexposed cohort) will be formed for the final analysis of pregnancy outcomes (Table 1). To be eligible for either cohort, pregnant women must be enrolled from 12 months before cohort entry (ie, the index date) until the end of pregnancy.

Table 1. Cohort definitions for analysis of pregnancy outcomes

Cohort	Eligibility criteria	Index date
Exposed cohort	
 Receipt of a dose of Pfizer-BioNTech bivalent COVID-19 Vaccine in the exposure window (as defined in Table 3) Continuous enrollment in the 12 months before the index date until end of pregnancy 	
 Date of vaccination
Unexposed cohort	
 No receipt of any COVID-19 vaccine in the exposure window (as defined in Table 3) Continuous enrollment in the 12 months before the index date until end of pregnancy Matched individually (in a ratio of at least 1:1) to exposed women on estimated pregnancy start (LMP, within pre-specified calendar intervals), maternal age, and US state (if feasible, or broader geographic region if not feasible) 	
 Equivalent of the gestational age at vaccination (in days) in the exposed match. For example, if an exposed individual was vaccinated at 28 weeks and 3 days of gestation, the index date for unexposed matches would be set to 28 weeks and 3 days after their LMP.

COVID-19 = coronavirus disease 2019; LMP = date of last menstrual period; US = United States.

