9.2.4.2. Pregnancy and birth outcomes

For analysis of pregnancy outcomes, pregnant women will be followed from the index date until the earliest of the following: end of pregnancy, latest gestational age at which an outcome can occur (applies only to stillbirth and preterm birth), or receipt of another dose of any COVID-19 vaccine other than Pfizer-BioNTech bivalent COVID-19 Vaccine ([Table 4](#)).

PFIZER CONFIDENTIAL

CT24-WI-GL02-RF02 4.0 Non-Interventional Study Protocol Template For Secondary Data Collection Study
 01-Jun-2022

For analysis of birth outcomes, infants will be followed for events from birth until 12 months after birth (for major congenital malformations) or until 1 month after birth (for small size for gestational age) (Table 4).

Table 4. Follow-up for pregnancy outcomes and birth outcomes

Safety event	Start of follow-up	End of follow-up
Pregnancy outcomes		
Spontaneous abortion	Index date (as defined in Table 1)	Earliest of the following: 
 • Occurrence of spontaneous abortion • 20 weeks of gestation (latest gestational age at which a spontaneous abortion can occur) • Other event marking the end of pregnancy (ectopic pregnancy or pregnancy termination); to be treated as competing events • Receipt of another dose of COVID-19 vaccine other than Pfizer-BioNTech bivalent COVID-19 Vaccine
Stillbirth	Index date (as defined in Table 1)	Earliest of the following: 
 • Occurrence of stillbirth • Other event marking the end of pregnancy (ectopic pregnancy, spontaneous abortion, pregnancy termination, or livebirth); to be treated as competing events • Receipt of another dose of COVID-19 vaccine other than Pfizer-BioNTech bivalent COVID-19 Vaccine
Preterm birth	Index date (as defined in Table 1)	Earliest of the following: 
 • Occurrence of preterm birth (ie, livebirth before 37 completed weeks of gestation) • 37 weeks of gestation (latest gestational age at which a preterm birth can occur) • Other event marking the end of pregnancy (ectopic pregnancy, spontaneous abortion, pregnancy termination, stillbirth); to be treated as competing events • Receipt of another dose of COVID-19 vaccine other than Pfizer-BioNTech bivalent COVID-19 Vaccine
Birth outcomes		

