9.5.2. Study size for the pregnancy cohort

Table 9 provides power calculations for pregnancy outcomes assuming a log-rank test at a 2-sided alpha = 0.05 level for various hazard ratios and numbers of pregnant women (1:1 matching ratio) for each birth outcome assuming the incidence of each outcome is 0.5% for stillbirths, 10% for preterm, and 12% for spontaneous abortion.

Table 9. Power for varying hazard ratios and study size for pregnancy outcomes

Outcome (incidence)	Number of pregnant women per group	Hazard ratio			
		1.2	1.6	2	2.4
Stillbirths (0.5%)	20,000	0.269	0.959	1.000	1.000
	40,000	0.475	0.999	1.000	1.000
	60,000	0.642	1.000	1.000	1.000
	80,000	0.765	1.000	1.000	1.000
	100,000	0.851	1.000	1.000	1.000
Preterm (10%)	20,000	1.000	1.000	1.000	1.000
Spontaneous abortion (12%)	20,000	1.000	1.000	1.000	1.000

For example, assuming the true HR = 1.2, an outcome (eg, stillbirth) with a rate of 0.5% during follow-up, and a sample size of 100,000 per group, there would be 85% power to reject a null hypothesis of HR = 1.0. A sample size of 20,000 per group provides a power of 100% for preterm and spontaneous abortion if the true HR is 1.2 or higher.

For the birth outcomes (i.e., small size for gestational age and major congenital malformations), assuming the true odds ratio = 1.2, an outcome rate of 3% in the unexposed group and a sample size of 20,000 per group, there would be 90% power to reject (at p = 0.05 level for a 2-sided test) a null hypothesis that the prevalence odds ratio = 1.0.

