9.7.2. Analysis of pregnancy and birth outcomes

Among pregnant women, the distribution of demographics, comorbidities, and other potential confounders will be reported and compared between the matched exposed and unexposed cohorts. Covariate balance in the matched and weighted cohorts will be assessed using standardized differences or other suitable methods.

Vaccinated pregnant women will be matched to pregnant unexposed comparators in a ratio of exposed:unexposed of at least 1:1 on maternal age, US state (if feasible, or broader geographic region if not feasible), and pregnancy start (to address confounding by calendar time). Confounding by other variables will be addressed using inverse probability of treatment weighting, based on propensity scores estimated in the matched population.

In each data RP, measures of incidence or prevalence of pregnancy and birth outcomes and associated 95% CIs will be estimated within the matched exposed and unexposed cohorts.

Cox models or Poisson regression will be used to calculate adjusted HRs or incidence rate ratios and 95% CIs for spontaneous abortion, stillbirth, and preterm birth. For major congenital malformations and small size for gestational age, logistic regression will be used to estimate PORs and 95% CIs.

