Similar to other claims and electronic health records databases in the US, an additional limitation of the data sources proposed for this study is that a substantial proportion of individuals may lack enrollment from the initial authorization of COVID-19 vaccines (on 10 December 2020) until the index date; long-term enrollment would be necessary to definitively assess prior completion of a primary vaccine series based on a patient's recorded history of COVID-19 vaccines in claims/administrative data. Within the Sentinel Distributed Database, only 47% of individuals have ≥ 2 years continuous database enrollment, with 36% of individuals enrolled for at least 2.5 years (Sentinel, 2023b). This may severely limit the ability to identify receipt of the bivalent vaccine as a primary series versus booster dose.

Another data source–related limitation is that the identification of outcomes and covariates in claims data and electronic health records data is based on algorithms and is subject to misclassification (eg, false positives, false negatives). There have been limited validation studies of *International Classification of Diseases, 10th Revision, Clinical Modification* (ICD-10-CM)-based algorithms for safety events of interest, and the accuracy of algorithms for many safety events of interest is unknown. When possible, validated algorithms will be used. However, some events, such as spontaneous abortion, are particularly at risk of misclassification, because early pregnancy losses may not be recognized in claims or even by the individual. If prior studies have not demonstrated adequate performance of the algorithm for myocarditis/pericarditis, a quantitative bias analysis will be performed to assess the potential impact of outcome misclassification on comparative risk estimates for myocarditis/pericarditis based on ongoing validation studies. Capture of non-severe and asymptomatic COVID-19 is anticipated to be substantially incomplete due to the high prevalence of at-home testing, non-medically attended COVID-19, and incomplete capture of laboratory results in the Sentinel Distributed Database. History of COVID-19 (which is a covariate and subgroup of interest for the study) will therefore be limited to severe COVID-19, defined using inpatient diagnoses of COVID-19.

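### Enrolment required to the end of pregnancy retains early losses more readily than ongoing pregnancies, so spontaneous abortion incidence is overstated and no planned analysis shows by how much

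*Protocol*

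**What the plan says.** Section 9.2.2 sets the rule for both cohorts, and both rows of Table 1 repeat it: "pregnant women must be enrolled from 12 months before cohort entry (ie, the index date) until the end of pregnancy". Section 9.2.1.2 adds a second condition on the future: women are "eligible for inclusion in the final analysis of pregnancy and birth outcomes if they had a recorded pregnancy outcome" during the study period.

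For spontaneous abortion, Table 4 (Section 9.2.4.2) stops follow-up no later than "20 weeks of gestation (latest gestational age at which a spontaneous abortion can occur"). It has no row for leaving the health plan.

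Section 9.7.2 promises that, in each data partner, "measures of incidence or prevalence of pregnancy and birth outcomes and associated 95% CIs will be estimated" in the matched cohorts, and research question 2 is itself worded as a question about incidence.

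On plan turnover, Section 9.9 reports that in the Sentinel Distributed Database "only 47% of individuals have ≥ 2 years continuous database enrollment, with 36% of individuals enrolled for at least 2.5 years".

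**The concern.** The end of the required enrolment is the end of the pregnancy, and for these outcomes that is the event itself. The rule thus selects on the future, and its demands differ by outcome. The mismatch is plainest for spontaneous abortion. A woman who passes 20 weeks without a loss has completed all her at-risk time under Table 4, yet she is deleted if she leaves the plan at week 30. A woman with a loss at week 10 had to stay only until then. Events are kept while event-free pregnancies are removed.

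Nothing planned corrects this. Under Table 7, footnote d, propensity scores use information up to the index date (multiple pregnancy excepted), so the weights cannot undo selection that happens afterwards. The sensitivity analyses in Section 9.7.3 cover risk intervals, exposure misclassification, confounding and outcome misclassification, but not this. Section 9.9 says that the approach minimizes the selection bias that primary data collection might bring, and does not mention selection on remaining enrolled.

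At stake are the reported incidence of spontaneous abortion and, if women leave plans at different rates in the two arms, the hazard ratio.

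**Working it through.** **The plan's own figure first.** Section 9.5.2 works "assuming a log-rank test at a 2-sided alpha = 0.05 level" and "assuming the incidence of each outcome is 0.5% for stillbirths, 10% for preterm, and 12% for spontaneous abortion". For stillbirth, HR 1.2 and 100,000 per group, Table 9 gives power 0.851; the Schoenfeld formula gives 0.856 and the Freedman formula 0.854. Table 9 is sound and this point does not touch it. The 12% is used below as the true risk.

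**Turnover (c, exits per person-year).** The protocol gives no rate for pregnant women and none by arm. The figures in Section 9.9, under a constant hazard, imply:
- over the first 2 years: −ln(0.47)/2 = 0.38 per year
- between 2 and 2.5 years: −ln(0.36/0.47)/0.5 = 0.53 per year

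These describe all members, not women who already have 12 months of enrolment, so 0.53 is treated as an upper bound. Values of 0.1 and 0.2 are assumptions.

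**Model (assumptions).** Index at week 6; losses spread evenly over weeks 6 to 20; all other pregnancies end at week 39; exit unrelated to outcome.
- Share of non-losses kept: N = exp(−c × 33/52.18)
- Share of losses kept: L = (1 − e^(−x))/x, with x = c × 14/52.18
- Incidence among retained pregnancies = 0.12 L / (0.12 L + 0.88 N)

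| c per year | L | N | Incidence read (true 12%) | Rate multiplied by |
|---|---|---|---|---|
| 0.10 | 0.987 | 0.939 | 12.5% | 1.05 |
| 0.20 | 0.974 | 0.881 | 13.1% | 1.10 |
| 0.38 | 0.951 | 0.786 | 14.2% | 1.20 |
| 0.53 | 0.932 | 0.715 | 15.1% | 1.28 |

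For c = 0.10: 0.12 × 0.987 = 0.1184; 0.88 × 0.939 = 0.8261; 0.1184/(0.1184 + 0.8261) = 0.125.

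**Hazard ratio under a true null.** The bias is the ratio of the two arms' rate multipliers.
- Equal turnover: 1.00. With equal turnover of 0.38 and a true HR of 1.2, the estimate is 1.198.
- Exposed 0.1, unexposed 0.2: 1.048/1.098 = 0.95. Reversed: 1.05.
- Exposed 0.2, unexposed 0.4: 0.91. Reversed: 1.10.

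**Other outcomes.** At 0.1 to 0.2 per year, stillbirth incidence is multiplied by 1.02 to 1.04 and preterm birth by 1.01 to 1.02. For 0.1 versus 0.2 per year, the null HR is 0.98 for stillbirth and 0.99 for preterm birth.

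**The case against.** Four points can be made for the plan.

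**The missing disenrolment row is not an oversight.** A reader might infer that Table 4 forgot censoring at plan exit. It did not: given the enrolment rule and the recorded-outcome condition, nobody in the cohort can leave during follow-up. Most women who leave mid-pregnancy would have no recorded outcome in any case. This stands. The selection sits in eligibility, and deleting the enrolment clause alone would not remove it.

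**The hazard ratio need not be biased.** Primary objective 2 is the relative risk. A reader might infer that the design makes the vaccine look protective because unvaccinated women change plans more often. The protocol has no figure for that, and the reverse gap gives bias the other way. Both arms need 12 months of prior enrolment, are matched on pregnancy start, age and state or region, and are weighted on prior healthcare use. This does not guarantee equal turnover, but it makes a large gap less plausible.

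**The size can be exaggerated.** Placing every loss at week 9 and applying 0.53 per year gives 0.12/(0.12 + 0.88 × 0.736) = 15.6%, which is not a fair central figure. Nor can a biased HR be turned into a confident false positive from 20,000 women each carrying the full 12% risk. That number is a power scenario in Table 9, and vaccination may come as late as 19 weeks and 6 days, after part of the risk has passed. This stands too.

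**A fixed span is not free of bias.** It conditions on enrolment after the loss. Section 9.2.1.1 itself warns, for prior vaccination history, that long enrolment requirements cut numbers and may bring selection bias. This is why a fixed span is not proposed as the primary rule.

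None of these removes the overstatement of incidence, which needs only some turnover.

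**Conclusion.** The point holds for spontaneous abortion incidence. The text fixes an enrolment requirement whose length depends on the outcome, and no planned weighting or sensitivity analysis addresses it. A true 12% reads about 12.5% to 13.1% at assumed turnover of 0.1 to 0.2 per year, and about 15% at the whole-database upper bound. These figures rest on the assumed index week, timing of losses and delivery at week 39.

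For the hazard ratio the point is conditional: no material bias with equal turnover, and bias in either direction if turnover differs. The documents supply neither the size nor the sign of any difference. For stillbirth and preterm birth the effect is small. This calls for a sensitivity analysis and plain reporting, not for replacing the primary eligibility rule.

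**What to change.** Keep the primary rule in Table 1, and make three additions.

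1. In Section 9.7.3 and Table 10, pre-specify a sensitivity analysis for spontaneous abortion that applies one enrolment span to every pregnancy however it ends: 12 months before the index date through LMP + 40 weeks, death excepted. Where a data partner can identify pregnancies before their outcome, an alternative is entry on information known at index with censoring at disenrolment. In the model above, this recovers 12.0% and a null HR of 1.00 if exit is non-informative.
2. Report by arm how many pregnancies the enrolment rule removes, where they can be identified. This shows directly whether the hazard ratio is threatened.
3. State this selection as a limitation in Section 9.9.

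The cost is some eligibility wording and one more query run. The fixed span discards some losses. With 30 weeks between a loss at week 10 and LMP + 40 weeks, the share is 1 − exp(−c × 30/52.18): about 6% at 0.1, 11% at 0.2 and 26% at 0.53 per year. Table 9 shows power of 1.000 for spontaneous abortion at 20,000 per group, so a sensitivity analysis can bear this if the cohort approaches that size. The fixed-span analysis also assumes that leaving the plan is unrelated to how the pregnancy ended, and the report should say so.
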